10.4 Blinding

The independent wound expert measuring the wound area will receive the wound images without participant identification data or study visit data and he/she will therefore be blinded when measuring the wound area and assessing the healing status of the wound.

10.5 Interim Analysis for Sample Size Adjustment

An interim analysis will be conducted when approximately 60% have been enrolled.

The Interim Analysis will be directed and conducted by an independent statistician who is not involved in the study conduct other than the Interim Analysis. The main purpose of this Interim Analysis is to validate the assumptions in calculating the sample size (i.e., the effect sizes assumed in the initial sample size calculations). Using the observed difference of percentage reduction in area, and all other original assumptions noted above, the independent statistician will re-calculate the sample size. Based on the documented sample size re-calculation and the observed drop-out rate, the independent statistician's report will either recommend a new, increased sample size sufficient to achieve the study's objectives or will provide documentation that the current sample size is sufficient with no need to increase the sample size.

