10.5.1 Procedure for Interim Analysis

The data to be used in the interim analysis and the treatment assignment of each randomised subject will be given to the statistician. Using this data, the independent statistician will calculate the following metrics for the primary end point:

1. Mean and standard deviation of LHR in each group.
2. The dropout rate at the time of the Interim Analysis, IA
3. The statistical power of the trial at the time of the IA (using a conditional power approach).
 - a. If the statistical power is larger than 50%, then the sample size will be adjusted upward and no Type I error rate adjustment will be made to the final analysis.
 - b. If the statistical power is less than 50%, the Type I error rate will be inflated and statistical adjustment will be made to the final analysis if the decision to increase the sample size is made. That is, the observed p-value, as well as the point estimate of the response rates, and the 95% CIs will be based on:

$$p\text{-value} = 2 * \{1 - T_2(n_1+n_2 - 1) (|z_1 + z_2|/\sqrt{2})\},$$

Healing rate for each treatment group: $\hat{S} = (\sqrt{n_1} \times \hat{S}_1 + \sqrt{n_2} \times \hat{S}_2) / (\sqrt{n_1} + \sqrt{n_2})$,

95% Confidence Intervals = $(\hat{S} - 2 \text{ta}/2:2(n_1+n_2 - 1)\sigma, \hat{S} + 2 \text{ta}/2:2(n_1+n_2 - 1)\sigma)$

where n_1 is the sample size in the treatment group before interim analysis and n_2 is the sample size in treatment group after the interim analysis; $T_2(n_1+n_2 - 1)$ (.) is t distribution with $2(n_1+n_2-1)$ degrees of freedom. The \hat{S}_1 is the healing rate of the n_1 observation before the interim analysis and \hat{S}_2 is the healing rate of the n_2 observation after the interim analysis. The $(\sqrt{n_1} + \sqrt{n_2})\sigma$ is the observed pooled standard deviation before and after the interim analysis.

4. Using the observed metrics above, along with Type I Error Rate of 0.05, the sample size will be re-calculated and the independent statistician will provide the following to the sponsor and the statistician responsible for the trial:
 - a. Re-estimation of sample size using the observed rate of healing and dropout rate
 - b. The difference in percentage of healed subjects
 - c. The healing rate in Treatment arms
 - d. The healing rate in the Control arm
 - e. The power used in calculating the new sample size

No other information will be shared with the sponsor or the statistician responsible for this trial.

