10.5.2 Results of Interim Analysis

The new sample size calculation is:

Based on a pair-wise comparison of geko™ 12h run-in vs treatment:

From the interim data, there is a mean difference of 0.58 mm/week between run-in and treatment and a standard deviation of 0.97 mm/week.

Assuming requirements of 80% power and $p=0.05$ (2-sided) 25 subjects would be needed in the geko™ 12H group. (30)

Little benefit is foreseen in continuing the geko™ 6h group, as statistical significance is not expected at the projected number of subjects in this trial.

From the results of the Interim Analysis the new Treatment Groups are:

Group	Description
SC	Standard care (multilayer, multicomponent compression intended for the treatment of VLU)
geko 12h	geko™ version XW, W-3 or variant (12 h daily neuro-stimulation) and SC

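### Section 10.2 still gives a size and power for a removed arm, and 10.5.2 does not say that its smaller size and arm drop fall outside the interim rule

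*Combined protocol and SAP*

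**What the plan says.** **Size.** Section 10.2 gives 35 evaluable per group, 90% power to show an effect at the lower dosage, and 126 randomised (42 in each of three groups). The synopsis and 3.1.1 say 60 randomised. Section 10.6 lists two groups, SC and 12h.

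**Interim rule.** Under 10.5 the report recommends an increased size or "will provide documentation that the current sample size is sufficient with no need to increase the sample size". The statistician receives the treatment assignments (10.5.1). Above 50% conditional power, "then the sample size will be adjusted upward and no Type I error rate adjustment will be made to the final analysis". Below 50%, "statistical adjustment will be made to the final analysis if the decision to increase the sample size is made". Item 4e has the statistician report "The power used in calculating the new sample size".

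**What was done.** Section 10.5.2 takes the 12h within-arm difference between run-in and treatment, 0.58 mm/week with SD 0.97. At 80% power and two-sided 0.05 it concludes that "25 subjects would be needed in the geko™ 12H group". It stops the 6h arm, "as statistical significance is not expected at the projected number of subjects in this trial".

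**Interim variable.** Section 10.5 instructs: "Using the observed difference of percentage reduction in area, and all other original assumptions noted above". Section 10.5.1 item 1 asks for "Mean and standard deviation of LHR in each group", and 10.5.2 reports a healing rate in mm/week.

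**Final tests.** Section 10.12.1 names Wilcoxon signed rank within groups and Mann-Whitney between groups, with no reference to the interim.

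**The concern.** Three things are at stake.

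- **Section 10.2 is out of date.** A reader who goes to the sample size section finds a total and a power that no longer apply, the latter attached to an arm that no longer exists. Nothing marks the text as superseded.
- **The adaptation has no printed rule.** A decrease and an arm drop are in neither branch of 10.5.1. Section 10.5.2 gives no conditional power and does not say whether any adjustment applies. The protocol is therefore silent on how the final 12h test treats a size chosen from data that also enter that test.
- **The 80% may be read as covering the objective.** The objective is 12h plus SC against SC alone. The calculation in 10.5.2 covers only the change within the 12h arm.

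**Working it through.** **1. Reproduce the 25.** Inputs from 10.5.2: difference 0.58, SD 0.97, power 80%, two-sided 0.05.

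- d = 0.58/0.97 = 0.598.
- Normal approximation: n = ((1.960 + 0.842)/0.598)² = 21.95, so 22.
- Noncentral t (non-centrality d√n, n − 1 df): power is 80.1% at 24 and 81.8% at 25 (non-centrality 0.598 × 5 = 2.99).
- Dividing 24 by the signed-rank efficiency of 0.955 gives 25.1. Simulated signed-rank power at 25 is about 80%.

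The 25 is sound for the comparison that it names.

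**2. Compare the totals.**

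| Source | Evaluable per group | Groups | Randomised |
|---|---|---|---|
| 10.2 | 35 | 3 | 126 (35 × 1.2 = 42; 3 × 42) |
| 10.5.2 | 25 (12h only) | 2 | not stated |
| Synopsis, 3.1.1 | not stated | 2 (synopsis) | 60 |

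2 × 25 × 1.2 = 60 suggests two arms of 30, but the text does not say so. Nor does it say whether patients already randomised to 6h count toward the 60. That matters: 10.5 times the interim at about 60% enrolled. If this means 60% of 126, then 0.6 × 126 is about 76, more than the new total. Enrolled may include patients still in run-in, so the text has to say who counts.

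**3. Set the rule beside the action.**

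| Change | Covered by 10.5 or 10.5.1? |
|---|---|
| Increase, conditional power above 50% | Yes, no adjustment |
| Increase, conditional power below 50% | Yes, adjusted p-value, estimate and interval |
| No change | Yes |
| Different power used in the calculation | Possibly foreseen (item 4e) |
| Decrease | No |
| Arm dropped | No |

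Section 10.5.2 made the last two changes.

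**4. Power for 12h versus SC.** The documents give no SC change or SC SD. Assume no change on SC, SD 0.97 in both arms and 1:1 allocation.

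- Normal approximation, 25 per arm: 0.58/(0.97 × √(2/25)) = 2.11; Φ(2.11 − 1.96) = 56%.
- The same at 30 per arm: 0.58/(0.97 × √(2/30)) = 2.32; Φ(2.32 − 1.96) = 64%.
- Mann-Whitney, the planned test, by simulation: about 51-52% at 25 and 60% at 30 per arm. About 48 per arm gives 81%.
- If SC improves so that the difference is 0.40: about 28% at 25 and 33% at 30.

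**5. Error from re-sizing alone.** The interim numbers are not printed. Assume 15-25 interim patients in the 12h arm, a cap of 35 or 42, and size re-set for 80% power at the observed effect. With no true effect and an unadjusted pooled test, the favourable-direction error (nominal 2.5%) is:

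| Test and rule | Simulated error |
|---|---|
| Signed rank, at least 5 later patients | 2.6-3.0% |
| Paired t, at least 5 later patients | 2.6-3.2% |
| Paired t, no minimum of later patients | 2.7-3.3% |

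The range across these settings is 2.6-3.3%. It does not include any effect of dropping an arm.

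**The case against.** **The text can be read as history.** Section 10.5.2 calls its calculation new, so 10.2 might be taken as the original rationale. Sections 10.1 and 10.12 also defer detail to a separate SAP, which was not available for this review and may address the final test. Both points are fair. But 10.2 is current protocol text with no such label, and a SAP would not correct it.

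**The sizing follows the primary endpoint.** Section 10.7.1 evaluates each regimen by the within-group paired comparison and treats the between-group comparison as additional. This stands: sizing on the paired comparison is not an error. What is missing is a statement that the 80% does not extend to the objective.

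**The inflation is small.** This also stands, and it is why disclosure is enough.

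Three stronger readings are tempting, and the documents do not support them:

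- *The interim should have ended in a finding that the size was sufficient.* At the interim 12h effect, 35 per group has 93.0% power by paired t, so a reader might infer this. But 10.2 sized the 35 for the lower dosage, and 10.5.2 says significance was not expected there. Neither the 6h estimate nor the conditional power is printed, so which outcome 10.5 called for cannot be known.
- *The arm drop roughly doubles the error.* If the better of two active arms were always carried forward, simulated favourable-direction error would be 4.8-5.4%. That is an upper scenario. The reason printed is lack of promise at 6h, not selection of the better arm.
- *The equal-weight combination in 10.5.1 should now be applied.* It would lower signed-rank power at 25 evaluable from about 80% to 70% if 20 were already in the interim. It needs a fallback when few later patients remain. With that fallback the error is about 2.7-2.9%, against 2.7-3.3% unadjusted, and slightly worse than no adjustment at 25 interim patients with a cap of 35. It would also rewrite a procedure after unblinding, and it does not address the arm drop.

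**Conclusion.** The concern holds as a matter of inconsistent and incomplete protocol text. Section 10.2 contradicts 3.1.1, 10.5.2, 10.6 and the synopsis. The decrease and the arm drop are outside the printed rule and are not identified as such. The new size supports about 80% power for the within-arm 12h comparison only, and the stated objective has roughly 50-60% under favourable assumptions (no change on SC, SD 0.97, 1:1 allocation).

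The effect of re-sizing on the error rate is minor: 2.6-3.3% against 2.5%, resting on assumed interim sizes. The effect of the arm drop cannot be quantified from the documents. The contradictions between sections are certain; confidence in the magnitudes is medium. The corrections should be made, but nothing here shows that the figure of 25 is wrong or that the final result would be invalid.

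**What to change.** 1. **Section 10.2.** Replace the figures with 60 randomised, the number per arm, and whether patients already randomised to 6h count toward the 60. State about 80% power at 25 evaluable (paired t 82%, signed rank about 80%) for the within-arm 12h run-in versus treatment comparison only. State that 12h versus SC is not powered at 80%: Mann-Whitney about 51-52% at 25 and 60% at 30 per arm, with the assumptions in step 4 of the working, and about 28-33% if the difference is 0.40.
2. **Section 10.5.** Change percentage reduction in area to LHR.
3. **Section 10.5.2.** State that the reduction and the arm drop were outside the prespecified rule, that the 12h size was set from interim data that also enter the final test, and that the nominal level is therefore not assured. Add that the inflation from re-sizing alone is expected to be small (about 2.6-3.3% in the favourable direction against 2.5%, for assumed interim sizes of 15-25 per arm), and that this range does not include any effect of the arm drop. Leave 10.5.1 as it stands, and do not add a combination test.

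The cost is a wording amendment. It needs no extra patients, loses no power and adds no analysis. The sponsor must supply the per-arm numbers and the status of the 6h patients, which the documents do not give.

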10.5.1 Procedure for Interim Analysis

The data to be used in the interim analysis and the treatment assignment of each randomised subject will be given to the statistician. Using this data, the independent statistician will calculate the following metrics for the primary end point:

1. Mean and standard deviation of LHR in each group.
2. The dropout rate at the time of the Interim Analysis, IA
3. The statistical power of the trial at the time of the IA (using a conditional power approach).
 - a. If the statistical power is larger than 50%, then the sample size will be adjusted upward and no Type I error rate adjustment will be made to the final analysis.
 - b. If the statistical power is less than 50%, the Type I error rate will be inflated and statistical adjustment will be made to the final analysis if the decision to increase the sample size is made. That is, the observed p-value, as well as the point estimate of the response rates, and the 95% CIs will be based on:

$$p\text{-value} = 2 * \{1 - T_2(n_1+n_2 - 1) (|z_1 + z_2|/\sqrt{2})\},$$

Healing rate for each treatment group: $\hat{S} = (\sqrt{n_1} \times \hat{S}_1 + \sqrt{n_2} \times \hat{S}_2) / (\sqrt{n_1} + \sqrt{n_2})$,

95% Confidence Intervals = $(\hat{S} - 2 \text{ta}/2:2(n_1+n_2 - 1)\sigma, \hat{S} + 2 \text{ta}/2:2(n_1+n_2 - 1)\sigma)$

where n_1 is the sample size in the treatment group before interim analysis and n_2 is the sample size in treatment group after the interim analysis; $T_2(n_1+n_2 - 1)$ (.) is t distribution with $2(n_1+n_2-1)$ degrees of freedom. The \hat{S}_1 is the healing rate of the n_1 observation before the interim analysis and \hat{S}_2 is the healing rate of the n_2 observation after the interim analysis. The $(\sqrt{n_1} + \sqrt{n_2})\sigma$ is the observed pooled standard deviation before and after the interim analysis.

4. Using the observed metrics above, along with Type I Error Rate of 0.05, the sample size will be re-calculated and the independent statistician will provide the following to the sponsor and the statistician responsible for the trial:
 - a. Re-estimation of sample size using the observed rate of healing and dropout rate
 - b. The difference in percentage of healed subjects
 - c. The healing rate in Treatment arms
 - d. The healing rate in the Control arm
 - e. The power used in calculating the new sample size

No other information will be shared with the sponsor or the statistician responsible for this trial.

10.5.2 Results of Interim Analysis

The new sample size calculation is:

Based on a pair-wise comparison of geko™ 12h run-in vs treatment:

From the interim data, there is a mean difference of 0.58 mm/week between run-in and treatment and a standard deviation of 0.97 mm/week.

Assuming requirements of 80% power and $p=0.05$ (2-sided) 25 subjects would be needed in the geko™ 12H group. (30)

Little benefit is foreseen in continuing the geko™ 6h group, as statistical significance is not expected at the projected number of subjects in this trial.

From the results of the Interim Analysis the new Treatment Groups are:

Group	Description
SC	Standard care (multilayer, multicomponent compression intended for the treatment of VLU)
geko 12h	geko™ version XW, W-3 or variant (12 h daily neuro-stimulation) and SC

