
1. Known allergy to any of the protocol-stipulated treatments, or non-tolerance of multilayer, multicomponent compression therapy intended for the treatment of VLU.2. History of significant haematological disorders (e.g. Sickle Cell disease).3. History of Deep Vein Thrombosis (DVT) within six months preceding study entry4. History of Pyoderma Gangrenosum or other inflammatory ulceration.5. Pregnancy or breast feeding.6. Use of investigational drug or device within four weeks prior to study entry that may interfere with this study.7. Use of any neuro-modulation device.8. Surgery during three months prior to study entry (such as abdominal, gynaecological, hip or knee replacement)9. Trauma to the lower limbs that would prevent geko™ from stimulating the common peroneal nerve.10. No involuntary movement of the lower leg/foot at the maximum tolerable device setting.11. Any medication deemed by the Investigator to potentially interfere with the study treatment (e.g. systemic steroids).12. Participation in any other clinical study.	

Name of Sponsor/Company: Firstkind Ltd, [name]	
Name of Study Product: geko™ neuromuscular stimulator	
Comparator Product: Multilayer, multicomponent compression therapy intended for the treatment of VLU (Standard Care)	

Statistical Analysis:**Sample Size Determination and Rationale:**

The new sample size calculation is:

Based on a pair-wise comparison of geko™ 12h run-in vs treatment:

From the interim data, there is a mean difference of 0.58 mm/week between run-in and treatment and a standard deviation of 0.97 mm/week.

Assuming requirements of 80% power and $p=0.05$ (2-sided) 25 subjects would be needed in the geko™ 12H group. (30)

Little benefit is foreseen in continuing the geko™ 6h group, as statistical significance is not expected at the projected number of subjects in this trial.

From the results of the Interim Analysis the new Treatment Groups are:

Group	Description
SC	Standard care (multilayer, multicomponent compression intended for the treatment of VLU)
geko 12h	geko™ version XW, W-3 or variant (12 h daily neuro-stimulation) and SC

Analysis Populations:

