1.6 Study Rationale, Benefits and Risks

This study is designed to evaluate the efficacy of two geko™ daily treatment durations in conjunction with Standard Care (SC), consisting of multilayer, multicomponent compression therapy intended for the treatment of VLU, compared with each other and to that of SC alone in participants with VLUs. geko™ has been shown to facilitate wound healing in earlier studies (See Section 1.5 Summary of prior clinical studies) and patients receiving the geko™ 6h or 12h daily in addition to SC may experience faster wound healing as well as greater pain reduction than patients treated with SC alone. We believe that treatment with geko™ will in conjunction with SC potentially lead to faster healing and re-epithelialisation than treatment with SC alone for patients with VLU.

A potential risk for participants randomised to the geko™ daily treatments is the possibility of eczema at the application site. This, however, is unlikely based on previous experience with geko™ (20). Potential adverse events for all research participants in this study are intrinsic to the nature of VLUs, including but not limited to: pain and infection at the wound site, and maceration of the surrounding skin.

Not all patients may respond to the geko™ stimulus. Therefore, patients with no involuntary movement of the lower leg/foot at the maximum tolerable device setting will be excluded from the study.

2 Study Objective

The objective of this study is to compare the efficacy of a daily geko™ device treatment durations of 12 hours, in conjunction with SC, to SC alone, in patients with venous leg ulcers.

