3.1 Study Population

3.1.1 Number of Participants

A total of 60 patients will be randomised into the study

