10.7 Description of Study Endpoints

10.7.1 Primary Efficacy Endpoint

The primary efficacy endpoint for the study is LHR from TV1 to EOT as compared with LHR from RV1 to TV1. LHRs will be measured by a blinded wound expert using digital images at RV1, TV1, EOT, and at HCV if scheduled.

Each participant will be used as his/her own control, i.e. a participant's healing trajectory before commencement of treatment will be compared to his/her healing trajectory after introduction of treatment.

Since significant non-homogeneity may be expected in VLU participants and their respective healing trajectories, a pre-treatment run-in phase will be used to allow each participant to be used as his/her own control, i.e. a participant's healing trajectory before introduction of treatment will be compared to his/her healing trajectory after introduction of treatment. This allows an intra-group pair-wise comparison to evaluate the efficacy of each treatment regimen.

Additionally, for each participant, it enables generation of a treatment healing rate normalised relative to an initial healing rate. Inter-group (albeit un-paired) comparisons based on this normalised value are likely to be more sensitive than comparison of raw healing rates.

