10.12.1 Efficacy Analyses

Primary Endpoint: The primary efficacy endpoint is linear healing rate (LHR) from TV1 to EOT as compared with LHR from RV1 to TV1. LHRs will be measured by a blinded wound expert using digital images at RV1, TV1, and EOT.

Within treatment groups, treatment phase will be compared to run-in phase by paired non-parametric test (Wilcoxon signed rank). Effects will be compared between groups using non-paired non-parametric tests (Mann-Whitney).

Secondary Endpoints:

Weekly LHR shall be compared as above.

EOT healing status between groups shall be compared by Mann-Whitney U test on the PWAT scores. Weekly LHR can be tested using the same method (and same wording) as final LHR. Incidence of healing shall be compared between groups using Fisher's exact test.

Intra-group pain reduction measured on a visual analogue scale (VAS) will be analysed using paired t-test.

Inter group differences in time to clinically significant reduction in VAS shall be tested using Mann-Whitney u-test.

Intra-group changes to both Quality of Life (QoL) instruments in the study (CWIS and EQ-5D-5L) shall be tested using Wilcoxon signed rank test.

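### The current sample size (25 patients, 80% power) is for a before/after test within the geko arm; power for geko versus standard care is not stated, and the plan does not say which test decides the objective

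*Combined protocol and SAP*

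**What the plan says.** - **Objective (Section 2 and synopsis).** The device, 12 hours daily, is to be compared "in conjunction with SC, to SC alone, in patients with venous leg ulcers". Section 3 randomises patients to those two arms.
- **Current sample size (Section 10.5.2 and synopsis).** It is "Based on a pair-wise comparison of geko™ 12h run-in vs treatment". The inputs are a mean change of 0.58 mm/week, an SD of 0.97 mm/week, 80% power and two-sided 0.05. The result is that "25 subjects would be needed in the geko™ 12H group". No SC change, SC SD, SC sample size or between-arm difference is given.
- **Total (Section 3.1.1).** "A total of 60 patients will be randomised into the study". The step from 25 to 60 is not shown, and no allocation ratio is stated.
- **Primary endpoint (Section 10.7.1).** Treatment-phase linear healing rate (LHR) is set against run-in LHR in the same patient. "This allows an intra-group pair-wise comparison to evaluate the efficacy of each treatment regimen". The comparison between groups follows as an addition, on a normalised rate whose form (difference or ratio) is not defined.
- **Analysis (Section 10.12.1).** Under the primary endpoint there is a Wilcoxon signed-rank test within each group and a Mann-Whitney test between groups. There is no order, success rule or statement of which one decides.
- **Older text (Section 10.2).** It still describes three groups, 35 per group, 90% power for the lower dosage and 126 randomised, with no note that it has been replaced.
- **SAP.** Sections 10.1 and 10.12 leave detail to a separate SAP that is not among the documents.

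**The concern.** A change from run-in to treatment within the geko arm combines any device effect with time trend, study care and possible regression to the mean. Using each patient as his or her own control removes stable differences between patients but none of these. Only the contrast with the concurrently randomised SC arm does.

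The plan sizes the trial on the within-arm change and describes that change as the evaluation of efficacy. Two consequences follow. A significant before/after result could be presented as success without geko having been shown to do better than SC. And a non-significant geko-versus-SC result could not be read against any planned power or detectable difference.

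**Working it through.** **Inputs.** From Section 10.5.2: mean change 0.58, SD 0.97 mm/week (read as the SD of the within-patient change), two-sided 0.05. From Section 3.1.1: 60 randomised. From Section 10.2: loss of at most 20%, not restated for the new calculation. Assumed, because the documents are silent: SC mean change, SC SD of change, 1:1 allocation, and all 60 in the two remaining arms.

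**1. The plan's own figure.** Paired comparison, d = 0.58/0.97 = 0.598. Normal formula: n = [(1.96 + 0.842) × 0.97/0.58]² = 21.95; adding 1.96²/2 gives 23.9, so 24. Power by noncentral t with noncentrality d√n:

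| n | Power |
|---|---|
| 24 | 80.1% |
| 25 | 81.8% |
| 30 | 88.6% |

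The 25 is sound for the within-arm test.

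**2. The same inputs between arms.** Noncentrality = Δ/(0.97 × √(2/n)), with 2n − 2 degrees of freedom. For Δ = 0.58 (SC unchanged) it is 2.32 at 30 per arm and 2.07 at 24 per arm (60 × 0.8 / 2).

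| Per arm | Power |
|---|---|
| 20 | 45% |
| 24 | 53% |
| 25 | 54% |
| 30 | 62% |
| 45 | 80% |

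The planned Mann-Whitney test, in 20,000 simulated trials with normal data, gives about 50% at 24 per arm and 60% at 30 per arm. The difference detectable with 80% power (t test) is 0.80 mm/week at 24 per arm and 0.71 at 30 per arm.

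**3. Sensitivity to the assumptions, 24 to 30 per arm.**

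| Assumption about SC | Net difference | Power |
|---|---|---|
| Slows by 0.2 mm/week | 0.78 | 78–86% |
| No change | 0.58 | 53–62% |
| Improves by 0.2 | 0.38 | 26–32% |
| Improves by 0.29 (half of 0.58) | 0.29 | 17–21% |
| No change, SC SD 0.5 (Welch) | 0.58 | 72–81% |
| No change, SC SD 1.2 (Welch) | 0.58 | 44–53% |

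A 40:20 split with no loss and no SC change gives 57%. If a third of the 60 were patients already randomised to 6h, the 20-per-arm row in step 2 applies.

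**4. What the within-arm test does with no device effect.** Suppose patients improve from run-in to treatment for other reasons by 0.1 or 0.2 mm/week (assumed), with SD 0.97. At n = 25 the paired t test is then significant in 8% or 17% of trials, not 5%.

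**5. Section 10.2 does not fill the gap.** Its 90% is for the dropped lower dosage. Nor does it follow from its inputs: half of 0.80 is 0.40, and n = 35 then gives 63% for a paired test or 38% for a two-sample test. No test is named there.

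**The case against.** The strongest reply is that the primary endpoint is defined as a within-patient contrast, so the sample size matches the endpoint. On that reading only the match with the objective is missing. The same paired test is also applied to SC, so the SC change will be seen. This is fair as a description, but it confirms the problem: two separate paired tests do not test the difference between arms, and the objective is that difference.

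Second, the Mann-Whitney test is already listed, and the separate SAP could rank the tests and define the variable. It could. The documents at hand do neither, and the protocol's own sizing points to the within-arm test.

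Third, 60 can be reconstructed. Section 10.2 goes from 35 to 42 per group, a factor of 1.2, and 25 × 1.2 × 2 = 60. This is plausible and favours 1:1 allocation with all 60 in the two current arms, so the 20-per-arm and 40:20 cases are less likely. It remains inference, and it still gives no between-arm power (54% at 25 per arm if SC is unchanged).

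Fourth, SC could slow and not improve, in which case power could reach 80% or more. That stands: a shortfall is likely under the simplest assumption but is not proven.

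Fifth, the interim section announces a new calculation and the amendment log records removal of the 6h arm, so the unlabelled Section 10.2 is largely an editorial matter. That also stands.

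**Conclusion.** The concern holds and should be corrected before database lock. Three things are certain from the text: the 80% power belongs to a within-arm comparison, no power is given for geko versus SC, and the two tests under the primary endpoint are not ranked. None of these depends on an assumption.

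The size of the shortfall does. With SC unchanged, SD 0.97 in both arms and 1:1 allocation, power is 53–62%. Over the SC assumptions shown it runs from 17% to 86%, so true between-arm power is unknown from these documents. The SAP might settle the ranking of tests and the form of the between-arm variable, but it cannot be relied on unseen.

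**What to change.** 1. In Sections 2.1.1, 10.7.1 and 10.12.1 and in the SAP, before database lock, name the between-arm comparison of change in LHR (treatment minus run-in), geko 12h versus SC, as the test that decides the comparative objective. Define the variable as that difference. Make the within-arm signed-rank tests supportive and descriptive.
2. Record that this was settled after an interim analysis for which, under Section 10.5.1, "the treatment assignment of each randomised subject will be given to the statistician", and give the reason.
3. In Section 10.5.2 and the synopsis, say that 80% refers only to the within-arm test at n = 25. State between-arm power or the detectable difference, with the assumed SC change, SC SD, allocation and loss. Say how 60 was reached and whether it includes patients already randomised to 6h.
4. Mark the 126-patient, three-group, 90%-power text in Section 10.2 as superseded.

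**Cost.** Protocol and SAP text, with no extra patients and no new test. The stated power will look less favourable, and the deciding test will have been clarified after the interim. The changes disclose any shortfall without removing it; if the disclosed power is judged too low, the sponsor must choose between enlarging the trial and presenting the between-arm result as estimation.
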